## p. Procedure of data analysis and interpretation:

Data will be analyzed using computer based SPSS program (version 13.0). All data will be expressed as frequencies and mean ( $\pm$ SD or  $\pm$  SE). Comparison of symptom score between subgroups will be done by Student's unpaired t-test. Pearson's correlation test will be used to see correlation among different variables. P values less than or equal to 0.05 will be considered as significant.

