# **OBJECTIVES OF THE STUDY**

# **Primary Objectives:**

- To assess the effect of multistrain probiotics on abdominal pain using a validated symptom severity score in IBS patients.
- 2. To assess the efficacy of a multi-strain probiotic supplement as a treatment option for IBS in a tertiary referral centre

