# **Secondary Objectives:**

- To assess the effect of probiotics on global symptom severity scores which includes other symptoms of IBS (stool consistency, frequency, bloating) using a validated symptom severity score.
- 2. To assess changes in the use of rescue medication (i.e. laxatives or anti diarrhea medication such as Loperamide).
- 3. To assess any adverse events reported with probiotic use.

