### c. Main outcome variables to be studied:

Changes in abdominal pain for primary objective and overall symptom severity score as a secondary objective.

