### i. Sample Size:

For our trial, we will take equal sample size for both the groups  $(n_1 = n_2)$ . The sample size is to be determined using the following formula -

Sample size in each group,  $n_1$  = 2  $\sigma^2(Z_\beta + Z\alpha)^2 \, / \, (\mu_1 - \mu_2)^2$ 

Here,

 $Z_{\beta}$ = 0.84 at 80% power

 $Z\alpha = 1.96$  at 95% confidence interval

 $\mu_1$  –  $\mu_2$ = Minimum clinically important difference = 30 %( a minimal clinically significant reduction of 30% is desirable in probiotics group compared to placebo)

 $\sigma$  = Standard deviation = 87.77 (G. Sisson, et al. 2013)

Since there is no such study or trial carried out in Bangladesh, we could not find any reference value of Standard deviation of IBS-QOL or IBS-SSS scale among patients of Bangladesh. Hence we used a recent study (G. Sisson, 2013) to estimate the standard deviation.

The standard deviation found in the G. Sisson, et al. 2013 trial was 13.21 for IBS-QOL scale and 87.77 for IBS-SSL. Our study objectives include both the measures; hence we have considered the higher value of standard deviation so that the sample size is sufficient to cover both objectives.

Sample size in each group,  $n_1 = 2 \times (87.77)^2 \times (0.84 + 1.96)^2 / (30)^2$ 

= 135

Total sample size, n = 270

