#### **Outcome variables:**

According to the EMEA Guidance on the Evaluation of Medicinal Products for the Treatment of IBS, a responder is defined as a patient one whose abdominal pain score has improved at least 30 % compared to baseline.

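### The stated 80% power belongs to the IBS-SSS total, a secondary score; the primary abdominal pain outcome has no stated power and no single definition

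*Protocol*

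**What the plan says.** **Which outcome is primary.** Section c (Main outcome variables) assigns "Changes in abdominal pain for primary objective and overall symptom severity score as a secondary objective". The objectives agree. The first primary objective is "To assess the effect of multistrain probiotics on abdominal pain using a validated symptom severity score in IBS patients", and the first secondary one is "To assess the effect of probiotics on global symptom severity scores which includes other symptoms of IBS (stool consistency, frequency, bloating"). A second primary objective, the efficacy of the supplement as a treatment option for IBS, names no measure.

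**Form of the pain outcome.** Under Outcome variables, "a responder is defined as a patient one whose abdominal pain score has improved at least 30 % compared to baseline". The Rationale, drawing on EMEA guidance, asks for responder rates and ranks numerical change on scales as secondary. It also adds abnormalities of defecation to the primary outcome. Section c speaks of changes in pain and does not mention defecation.

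**Sample size (section i).** A two-means formula is used. The SD in the source trial "was 13.21 for IBS-QOL scale and 87.77 for IBS-SSL", and the larger value is taken: "hence we have considered the higher value of standard deviation so that the sample size is sufficient to cover both objectives". The difference is described as "a minimal clinically significant reduction of 30% is desirable in probiotics group compared to placebo" and entered as 30.

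**Analysis and timing.** Section p gives the between-group test: "Comparison of symptom score between subgroups will be done by Student's unpaired t-test". The abstract also lists chi-square, to be used where applicable. Scores are taken at baseline and months 1, 2 and 3. Month 3 falls after the 8 weeks of treatment, and no visit is marked as the deciding one.

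**The concern.** A power statement is useful only if it refers to the outcome that carries the trial's main claim. Here the two SDs considered are for quality of life and for the symptom scale, and neither is for abdominal pain. The claim that the size covers both objectives therefore says nothing about the primary one.

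The figure of 30% also serves two purposes. Under Outcome variables it is a within-patient threshold for response. In section i it is a between-group difference, and it enters the formula as 30 units beside an SD in score points. Used that way it is neither a 30% reduction nor a difference in responder rates.

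At stake is whether readers can take the 80% as applying to the main result, and which result that is: pain change or pain response, with or without defecation.

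**Working it through.** **1. Reproduce the plan's figure.** Inputs from section i: SD 87.77, difference 30, Z values 0.84 and 1.96.

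2 × 87.77² × (0.84 + 1.96)² / 30² = 134.2, so 135 per group and 270 in total. The plan's adjustment, 270 / (1 − 0.08 − 0.08)², gives 382.7. The protocol prints 384 and rounds up to 400. The arithmetic is sound to within rounding.

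**2. Identify the scale.** The data sheet records pain severity from 0 to 100% and pain days out of 10. A 0-100 item has a largest possible SD of about 50 (half the patients at each end). An SD of 87.77 therefore cannot be a pain-severity SD, and still less one for pain days. It fits the IBS-SSS total, which the protocol says runs from 0 to 500. Section i writes IBS-SSL and does not say total, so this is an inference, but no other scale in the protocol fits.

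**3. What the calculation does support.** For a 30-point difference on the total (normal approximation, two-sided 0.05):

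| n per arm | power |
|---|---|
| 135 | 80.2% |
| 184 (200 less 8% dropout) | 90.6% |
| 200 | 92.8% |

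**4. What the planned size gives for a pain responder.** The protocol gives no responder rates, so everything in this step is assumed: control rate p₁ of 30-60%, chi-square test, two-sided 0.05, n = 184 per arm. To carry the plan's effect over, read 30 as score points, so the shift is 30 / 87.77 = 0.342 SD. Then suppose that pain improvement is normal and shifts by the same amount: p₂ = Φ(Φ⁻¹(p₁) + 0.342). With p̄ the mean of p₁ and p₂,

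power = Φ{ [(p₂ − p₁) − 1.96 √(2p̄(1 − p̄)/n)] / √([p₁(1 − p₁) + p₂(1 − p₂)]/n) }.

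Example, p₁ = 0.40: p₂ = 0.535 and the difference is 0.135. The two standard errors are 0.0520 and 0.0515, so the argument is about 0.65 and the power 0.741.

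| p₁ | p₂ | difference (points) | power, n = 184 | difference with 80% power, n = 184 |
|---|---|---|---|---|
| 0.30 | 0.428 | 12.8 | 72.2% | 14.1 |
| 0.40 | 0.535 | 13.5 | 74.1% | 14.5 |
| 0.50 | 0.634 | 13.4 | 73.7% | 14.4 |
| 0.60 | 0.724 | 12.4 | 71.3% | 13.7 |

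If the 8% who drop out are instead kept among the 200 and counted as non-responders (both rates × 0.92), power is 65-71%.

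**5. Sensitivity.** At 184 per arm and the same control rates, a 15-point difference has 82-87% power and a 10-point difference 49-52%. If 30 was meant as a percentage, the 0.342 SD shift and the powers derived from it do not apply.

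**The case against.** **The t-test can serve the primary as section c words it.** Section c calls the primary a change in pain, and the protocol counts pain among the symptom scores, so an unpaired t-test on symptom score covers that reading. A 0.34 SD shift in a continuous pain score would have about 91% power at 184 per arm. This stands: the t-test is not an error, and the lower figures in step 4 come from dichotomising. It does not supply the missing basis, because the protocol gives no pain SD from which to judge whether 0.34 SD is the right shift.

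**Test and visit may be settled elsewhere.** A reader might infer that no test for responders exists and that the main result could be picked after the data are seen. The document does not support going that far. The abstract lists chi-square and refers to the effect of two months' use, which points to month 2. Matching tests and visits to outcomes is also commonly left to an SAP, which is not shown. The sizing on a secondary score is different, because it is written in the protocol itself.

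**The responder form might look like the reviewer's preference.** It is not: the Rationale calls for responder rates and ranks numerical change second, and Outcome variables defines only the responder. The Rationale is partly summarising guidance, however, so the protocol must still make the choice explicit.

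**The second primary objective is about general efficacy.** That blurs the split, but it names no measure and so does not make the total score primary.

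**Conclusion.** The point holds. The 80% power, and the 400 patients built on it, refer to a 30-point difference on the IBS-SSS total, which the protocol makes secondary. For abdominal pain, in either form, there is no SD, responder rate or power. The statement that the size covers both objectives is therefore unsupported for the primary. The definition of that primary also differs between the Rationale, section c and Outcome variables.

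A reader might infer that the trial is under-powered. That is not shown. The 71-74% rests on assumed control rates of 30-60%, normal pain improvement and a shift borrowed from another scale, and a 15-point difference would have more than 80% power. Nor is it fair to set responder power at 135 per group (58-61% for the same shift) against the stated 80%, since 135 is the size before the dropout adjustment and 200 per arm are to be enrolled. What can be said is that 80% power for response needs about 14 points (13.7-14.5) at 184 per arm, and that the protocol gives no figure against which to judge this.

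This should be corrected before unblinding, because it settles what the main claim is and what power lies behind it.

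**What to change.** - **State one primary:** the proportion with at least 30% improvement in a named abdominal pain score from baseline to month 2 (end of the 8-week treatment), compared between randomised arms by chi-square, with the difference and its 95% CI. Say whether the score is pain severity or pain days, since the data sheet records both.
- **Make secondary:** months 1 and 3, mean pain change and the IBS-SSS total.
- **Defecation:** say whether it belongs to the primary. Section c and Outcome variables imply that it does not, in which case correct the Rationale.
- **Second primary objective:** tie it to a measure or recast it as a general aim.
- **Sample size:** restate section i as the power of the planned 400 for the responder outcome, with the assumed control rate and difference written down. Keep the existing calculation, labelled as power for a 30-point difference on the IBS-SSS total (about 91-93% at 184-200 per arm), and correct the 30% label.
- **Align** the Abstract, Rationale, Primary Objectives, sections c, i and p, and Outcome variables.

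The cost is wording and a new power statement, with no new data and no more patients. Dichotomising loses some information, the stated power will look less favourable, and the secondary results can no longer carry the main claim. Adjusting the score analyses for baseline is an optional gain in precision, not part of the correction.

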#### **ABSTRACT**

**Background:** Irritable Bowel Syndrome (IBS) is a common functional gastrointestinal disorder. Common clinical manifestation include abdominal pain, bloating, altered bowel habit which bears a great impact on the quality of life of an individual. Previously limited number of studies carried out in our country to assess the effect of probiotics on IBS patients which yielded mixed results. Further study preferably with larger sample and longer duration was recommended. Aims and objectives: This study aims to see the effect of probiotics on IBS.

Material and method: This is a controlled randomized clinical trial. The patient will be selected on the basis of Rome III criteria. IBS patients with a sample size of 400 will be taken. Purposive non probability method of sampling will be employed. In this method the patients who will be readily available and in close proximity will be selected according to the selection criteria. Patient will be collected from gastroenterology outpatient department. After full explanation of the study procedure, informed written consent will be taken. Participants will be randomized to receive either probiotics (Biocult®, Sandooz Bd. Ltd.) with standard treatment or only standard treatment for 8 weeks. All participants will be interviewed with baseline symptom score. Similar interview for symptom score will take place at 1 month interval for 3 times (including 1 month post treatment). All data will be processed by the SPSS program values will be expressed as frequencies or mean±SD unless otherwise mentioned. Between groups analysis will be done by Chi-square test, unpaired or paired students t-test as applicable; while predictive values will be seen by regression analysis. Only P values <0.05 will be considered as significant.

**Result:** This study will see the effect of two months use of probiotics on IBS and thereby highlight over the longer treatment of IBS.

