#### RATIONALE OF THE STUDY

Many drugs have been advocated in the treatment of IBS, for instance, spasmolytics, bulking agents, psychotropic agents, and 5-HT receptor antagonists. However, in many cases all these options remain disappointing for the relief of symptoms. The therapeutic efficacy in IBS is probably impacted by the heterogeneous pathogenesis of the disease which includes altered intestinal motility, visceral hypersensitivity, abnormal brain gut interaction, food intolerance, altered intestinal permeability and post infectious changes. Recently, the adverse role of alteration of gut micro flora at the onset of symptoms has been emphasized. Therefore, rationale exists for the therapeutic use of probiotics in IBS. In 2004-2005 a randomized, double blind placebo controlled trial (Kabir MA et al, 2011) on the effect of S. boulardii in diarrhea predominant IBS patients was conducted at BSMMU but the result was not satisfactory. Another study (Rahman MZ et al, 2013) at BSMMU during 2010-2011 with multistrain probiotics yielded a beneficial outcome which was significant both clinically and statistically. On both occasions, further study was suggested preferably with a larger sample size. These recommendations for further study prompted this study to be carried out in order to assess the effect of multistrain probiotics in relation to change of symptom scores in IBS patients and also to see changes of quality of life before and after the treatment. As per EMEA guideline, previous study (Spiegel B et al, 2009) revealed that abdominal pain is the most prevalent and distressing symptom in IBS patients and changes in the severity of pain were reflected as a more reliable outcome of successful treatment. IBS shouldn't be diagnosed in the absence of abdominal pain or discomfort. The pain or discomfort is typically relieved by

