## Adjustment for non-compliance/cross-over

We also need to consider dropouts and poor adherence in calculating the sample size. It is estimated that around 5%-8% patients in both groups will drop out in different stages of the trial. The adjusted sample size is calculated based on the following formula –

Adjusted sample size,  $n_{adj} = n/(1-c_1-c_2)^2$ 

Here, n = 270

 $c_1$  = Dropout rate in control group = 8%

c2= Dropout rate in control group = 8%

Adjusted sample size,  $n_{adj} = 270 / (1 - .08 - .08)^2$ 

 $= 384 \approx 400$ 

The adjusted sample size in each group = 200

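### Continuous symptom scores are compared between the arms by an unadjusted t-test although the baseline score is collected: the test is valid, and only precision is lost

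*Protocol*

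**What the plan says.** Section p names one test for the symptom scores: "Comparison of symptom score between subgroups will be done by Student's unpaired t-test". It mentions no covariate and does not say whether the follow-up score or the change from baseline is tested. It defines no subgroups, so the word is best read as the two arms. The Abstract supports this: "Between groups analysis will be done by Chi-square test, unpaired or paired students t-test as applicable". The Abstract also mentions regression, but for another purpose: "while predictive values will be seen by regression analysis".

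The baseline value is available. The follow-up schedule, the procedures section and the data collection sheet in Appendix I all provide for scoring before treatment and then monthly, with the last assessment one month after treatment ends.

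On which variable matters most, the protocol points two ways. Section c gives "Changes in abdominal pain for primary objective and overall symptom severity score as a secondary objective", and the Rationale speaks of "change of symptom scores in IBS patients and also to see changes of quality of life before and after the treatment". The Rationale also says that the endpoints should be evaluated as responder rates and that numerical change on the scales is secondary. The outcome definition in section j is a responder, with at least 30% improvement in pain.

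**The concern.** When an outcome is measured before and after randomisation, the baseline value usually explains part of the variation at follow-up. A t-test on the follow-up score ignores it. A t-test on change uses it only by subtraction, which forces the baseline slope to be 1. ANCOVA estimates the slope from the data. With equal allocation it is at least as precise as either t-test, apart from the small cost of one extra parameter.

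What is at stake is the width of the confidence interval for the continuous pain and IBS-SSS comparisons. The protocol does not leave this open, because it names the test. A later analysis plan that used ANCOVA would depart from section p.

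**Working it through.** **Inputs from the protocol.** IBS-SSS SD 87.77 (Sample Size: "13.21 for IBS-QOL scale and 87.77 for IBS-SSL"); difference entered in the formula as 30; z-values 0.84 and 1.96; equal arms; 200 per arm enrolled and 8% dropout (Adjustment for non-compliance/cross-over), so 200 × 0.92 = 184 per arm with data. The 30 is labelled as a percentage ("a minimal clinically significant reduction of 30% is desirable in probiotics group compared to placebo"). It is read here as 30 points, as the formula uses it. Only the power figures depend on this.

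**Assumed, not in the protocol.** Baseline to follow-up correlation r = 0.3, 0.5, 0.7; ratio of follow-up SD to baseline SD k = 0.8, 1.0, 1.2. The protocol does not say whether 87.77 is the SD of a score or of change, so both are tried.

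**Plan's own figure.** 2 × 87.77² × (0.84 + 1.96)² / 30² = 134.2, rounded up to 135 per arm. The stated figure reproduces for an unadjusted comparison of two means.

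**Unadjusted t-test at 184 per arm.**
- SE = 87.77 × √(2/184) = 9.151
- 95% half-width = 1.96 × 9.151 = 17.94 points
- Power = Φ(30/9.151 − 1.96) = Φ(1.318) = 90.6%

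**Variance of ANCOVA relative to each t-test.**
- Against the follow-up score: 1 − r², whatever k is.
- Against change: k²(1 − r²) / (k² + 1 − 2rk), which equals 1 − (1 − rk)² / (k² + 1 − 2rk). It never exceeds 1, and it reaches 1 only when the baseline slope rk is 1.

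| ANCOVA variance relative to | r = 0.3 | r = 0.5 | r = 0.7 |
|---|---|---|---|
| t-test on follow-up score, any k | 0.91 | 0.75 | 0.51 |
| t-test on change, k = 0.8 | 0.502 | 0.571 | 0.628 |
| t-test on change, k = 1.0 | 0.65 | 0.75 | 0.85 |
| t-test on change, k = 1.2 | 0.762 | 0.871 | 0.966 |

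Estimating the slope costs a factor of about 1 + 1/(2 × 184 − 4) = 1.003 in variance.

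**Effect on IBS-SSS** (half-width = 17.94 × √ratio; SE = 9.151 × √ratio; power as above).
- Middle case, ratio 0.75 (r = 0.5, equal SDs): half-width 15.5, SE 7.925, power 96.6%.
- 87.77 as SD of the follow-up score, r = 0.3/0.5/0.7: half-width 17.1/15.5/12.8, power 93.0/96.6/99.6%.
- 87.77 as SD of change, most favourable (k = 0.8, r = 0.3, ratio 0.502): half-width 12.7, power 99.6%.
- 87.77 as SD of change, least favourable (k = 1.2, r = 0.7, ratio 0.966): half-width 17.6, power about 91.5%.

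In terms of patients, the middle case equals a t-test with 184/0.75 = 245 per arm, and the least favourable case one with 184/0.966 = 190 per arm. No SD is given for the pain score, so for pain the gain is known only as a variance ratio.

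**The case against.** The strongest reply is that nothing here is wrong. The t-test is valid, its power on the planning inputs exceeds the 80% target, and covariates are often settled in the analysis plan. The first two parts stand and set the severity. The third does not answer the point, because the protocol names a specific test.

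A second reply is that the Rationale ranks numerical change below responder rates, so only secondary analyses are touched. This stands in part. Section c makes change in pain the main variable, and the sample size is built on a comparison of two means. The protocol does not settle the ranking, and this point should not be presented as a fault in an undisputed primary analysis.

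A third reply is that the references to change in section c and the Rationale suggest a t-test on change, where the gain can be close to nil. That is correct for high r with a larger SD at follow-up, and the range above includes it. The equivalent of 245 patients per arm is one mid-range value and not the expected gain.

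A reader might also infer that omitting baseline biases the comparison or leaves the trial underpowered. The documents support neither. Randomisation makes the unadjusted comparison unbiased when data are complete, and power at the planning values is about 90.6%.

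**Conclusion.** The point holds as a free improvement of low severity. The protocol fixes a between-arm test that does not use baseline as a covariate, although the data for it are already collected. The cost is precision in the continuous pain and IBS-SSS comparisons and nothing else.

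Over the assumed ranges the IBS-SSS half-width falls from 17.9 points to somewhere between about 12.7 and 17.6, and power moves from 90.6% to between about 91.5% and 99.6%. These figures rest on an assumed correlation and SD ratio, on SD 87.77 applying to the variable tested, and on 184 patients per arm; the power figures also need 30 read as points. The direction does not depend on the assumptions: adjustment costs at most about 0.3% of variance.

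**What to change.** In section p, replace the t-test sentence with, for example: *Continuous abdominal pain score and IBS-SSS total will be compared between the randomised groups by ANCOVA with the baseline value of the same score as covariate, reporting the adjusted difference and its 95% CI.* Apply the model at each planned follow-up, and report the end of the 8-week treatment separately from the post-treatment month. Which time point is primary is a separate matter that this change does not decide. Bring the Abstract into line.

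The cost is wording only: no new data, visits or patients, and no change to the sample size.

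While the Abstract is open, the paired t-test listed under between-group analysis could be relabelled as a within-arm before-after description. That is a minor wording matter and not part of this point.
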